Short turn time	53	3.3
Length of duty	46	2.8
Rest quality	45	2.8
Schedule design	38	2.3
Trip length	37	2.3
Late duties	25	1.5
Fatigue calls	24	1.5
Length of flights	20	1.2
Rest - Circadian disruption	20	1.2
Deadhead	14	0.9
Total	1625*	

Note: * = total includes codes that did not fit a defined theme. Percentage column reflects the proportion of all codes counted within each theme.

Circadian disruption. This category includes all themes related to inconsistent schedules (*Circadian switches*), duties outside of daytime hours (*Redeyes, Early duties, Late duties, Out-of-hours work*), rest opportunities during the day (*Rest timing*), and rest breaks that involve a circadian switch between duties (*Rest – circadian disruption*).

The most common theme identified overall, *Circadian switches*, refers to changes in duty start times within a trip, for example switching from an early start time to a late start time. This theme was made up of codes including: CIRCADIAN SWAPS (34% of codes in this theme), INCONSISTENT DUTY TIMES

(25%), and SWITCHING TIME ZONES (18%). SWITCHING TIME ZONES refers to the sentiment that while a schedule may look consistent based on local departure times, similar local start times in different time zones could lead to circadian shifts of up to three hours. For example, a west coast-based pilot may start day 1 of a trip at 0600h on Pacific Time (PT) and then have a 0600h report time on day 2 on Eastern Time (ET), which is effectively 0300h PT.

High workload. This category includes all themes related to increased workload such as *High workload & hassle factors*, *Number of flights*, *Aircraft & crew swaps*, *Short turn times*, and *Length of flights*. The third most common theme identified overall was *High workload & hassle factors*, which refers to a collection of operational challenges contributing to fatigue. Often these factors add to overall workload through increased mental effort or creating time pressure and not allowing for mental recovery during or between flights. Some factors also extend duty times, leading to extended time awake and reduced rest opportunity. This theme was made up of codes including: WEATHER (30%), MAINTENANCE (19%), GROUND OPS (18%), and BUSY AIRPORTS/REGIONS (14%).

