Morning Sleep Diary. At the beginning of each day, participants will complete a sleep diary within the NASA PVT+ App. Each entry will include: wake-up time, a rating of sleep quality (5 -point scale from Extremely Good to Extremely Poor), the Samn-Perelli (SP) and Karolinska Sleepiness Scale (KSS), the location of their sleep, the timing and duration of any awakenings during the sleep period, and any additional information (i.e., notes).

Evening Sleep Diary. At the end of each day (right before sleep), participants will use the App to report the time they are going to sleep, the location of their sleep (e.g., home, hotel), if they used any caffeine during the day (amount used), any naps during the day (including timing and duration), timing/type of meals, and timing/type of exercise. Participants will also complete the SP and KSS and have an opportunity to provide any additional information about the day if necessary.

Flight Duty Period Data Collection. On flight duty days, participants will have additional entries and tasks to complete within the NASA PVT+ App (i.e., pre-duty, during flight, post-flight, and post-duty). Pre-duty entries will include: flight information, layover information, commute information, caffeine intake, the SP and KSS, and the Psychomotor Vigilance Task (PVT). During their flight, they will complete the SP, KSS, and the PVT, at or near the timing of TOD. Post-flight entries will occur within one hour of landing and will include flight information, the NASA TLX, report of fatigue countermeasures used, and hassle factors experienced (e.g., weather, air traffic control issues, traffic), SP, KSS, and PVT (if needed). Post-duty entries will include: duty information, operational factors (e.g., delays, sit times), overall fatigue rating (visual analog scale), KSS, SP, and PVT. Participants will also complete both the morning and evening sleep diary entries on flight duty days. Additional questions in the evening sleep diary on duty days include: commute information (i.e., timing, duration, and type of travel).

Table 2. Timing of data collection (repeated for one circadian-disruption trip and one trip without circadian disruption)

	1-3 Off-duty Days	Each Day of the Trip	1-3 Off-duty Days
Morn/evening Sleep Diary	✓	✓	✓
Sleepiness/ Fatigue	✓	✓	✓
Performance	✓	✓	✓
Workload		✓	
Duty information		✓	

[figure not shown]

Figure 3. Timing of flight day data collection

Tests and Scales

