Participant Recruitment. Members of fatigue risk management teams and union representatives across each airline will distribute recruitment material via e-mail and in safety newsletters to short-haul flight crew. When feasible, members of the study team may set up study information tables in the crew rooms at airports. Participation will be completely voluntary.

Participants will not be excluded based on race, ethnicity, or gender.

Sample Size. Based on previous studies in similar studies of chronic sleep loss compared to rested performance, we expect that the effect size for PVT lapses using a 5-minute PVT will be approximately 0.75. When accounting for the clustered nature of the study (i.e., four airlines), we estimate the inter-class correlation adjustment to be .015. As such, with an alpha level of 0.05 and 80% power, we estimate that we need 18 participants per condition (night flying or circadian switches), per airline for a total sample size of 36 participants per airline. In order to account for attrition after consent, unplanned schedule changes, and incomplete data collection, we would like to recruit up to an additional 15 participants per airline. This would result in a total sample size of 204 pilots.

Inclusion/Exclusion Criteria. All medically qualified, active-duty pilots currently flying short-haul operations are eligible to be included as participants in the study. Participants must be line pilots that spend at least 50% of their typical monthly schedule flying short-haul operations (defined as flights under 6 hours duration).

All flight crew who fly short-haul operations that meet the following study inclusion criteria will be eligible for participation.

Participants must be scheduled for and willing to collect data on each of the following:

- a. Trip with Circadian Disruption: A trip containing one of the following types of WOCL infringement:

- i. *Overnight FDPs.* An FDP in which the pilot is operating one or more flights through the WOCL (0200-0559h) relative to the pilot's home-base time or clock time.

OR

- ii. *Circadian Switching.* At least one FDP that starts between 0000-0659h relative to home-base time, followed by at least one FDP that ends between 0000-0659h, or *vice versa*, within the same trip (e.g., an FDP that begins at 0500h and the next FDP ends at 0100h or *vice versa*).

AND

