- b. Trip without Circadian Disruption: This trip must not contain any duties that are scheduled to begin or end between 0000h and 0659h relative to home-base time.

Proposed Test Schedule. Pending final decisions by the airlines regarding flights to be studied, the study is expected to commence in the summer of 2022.

12. Benefits of Participation

The results of this study may inform our understanding of how fatigue emerges during typical short-haul operations in the United States.

13. Possible Inconveniences, Discomfort, Pain, and Risks to the Participants

The risks associated with the protocol may differ from normal flying duties as follows:

It is possible that crew could experience slight discomfort and inconvenience from wearing an Actiwatch such as skin irritation or a rash, although no more than from wearing a wristwatch. An Actiwatch is the size of a wristwatch and is designed to be worn for weeks at a time.

Participants will record their performance using a handheld device employing the data collection app. Some crew could experience a degree of discomfort and inconvenience as the result of having their performance recorded for an extended period. Participants could be distracted from their flight duties while taking the tests, however, they will be instructed to take the test prior to the TOD, while still in the cruise phase when distractions are minimal.

Participants may also be inconvenienced by having to complete sleep, fatigue, and workload ratings. However, it is estimated that study information will only take about a total of 30 min in a day to record, with each phase of collection (e.g., pre-duty, evening diary) taking no more than 7 minutes.

As the study data will be archived at each airline or airline partner, it is possible that individual ID-coded data could be viewed or used by airline personnel.

14. Measures Taken to Minimize Discomfort and Risks

If the participant finds the actiwatch uncomfortable, then the study staff will work with the participant to determine if a different band could be used to minimize discomfort. If no acceptable alternatives are identified, then the participant will be free to discontinue wearing the device, which may require withdrawal from the study.

Participants will also be instructed to stop taking the PVT if they need to attend to their flying duties.

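### Do the two overlapping types of circadian disruption, with no quota for each, undermine the 18 + 18 = 36 pilots per airline?

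*Protocol*

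**What the plan says.** Section 11, Sample Size, takes an effect size of about 0.75 for PVT lapses, an alpha of 0.05, 80% power and an intra-class correlation adjustment of .015. It concludes that the study needs "18 participants per condition (night flying or circadian switches), per airline for a total sample size of 36 participants per airline". It then adds a reserve: "we would like to recruit up to an additional 15 participants per airline". The total is 204 pilots.

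The inclusion criteria in the same section admit a disrupted trip by either of two routes: "A trip containing one of the following types of WOCL infringement". Route (i), overnight duty, is "An FDP in which the pilot is operating one or more flights through the WOCL (0200-0559h", by home-base or clock time). Route (ii), circadian switching, is "At least one FDP that starts between 0000-0659h relative to home-base time, followed by at least one FDP that ends between 0000-0659h", or the reverse order, within one trip. The routes are joined by OR. Each pilot must also supply a trip without disruption, and Table 2 in section 9 shows the data collection "repeated for one circadian-disruption trip and one trip without circadian disruption".

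The aim (end of section 5) and the one hypothesis (section 8.1) compare disrupted with non-disrupted trips. Neither separates the two types or the four airlines.

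**The concern.** Each pilot contributes one disrupted trip, so 18 + 18 = 36 implies two separate groups of pilots in each airline. The eligibility wording does not form separate groups, because a trip can qualify by both routes and nothing says where it is then counted. Recruitment is open and voluntary, either route is enough, and the 15 reserve recruits are set per airline, not per type. The choice of flights is still open: "Pending final decisions by the airlines regarding flights to be studied". Section 5 also describes the focus-group theme of circadian switches differently; it "refers to changes in duty start times within a trip, for example switching from an early start time to a late start time", whereas route (ii) can be met by two identical overnight duties.

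If one type turned out rare, the 80% power stated per type and per airline would not be reached. The pooled estimate would average the two types in whatever mix arrived, and mixes that differ between airlines could make a type difference look like an airline difference. Analysts can classify trips afterwards, but they cannot recruit a type that is absent. The .015 adds some doubt, since it is described as clustering over four airlines while the sample size is set within one.

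**Working it through.** **The plan's own figures.** Inputs from section 11: effect 0.75, alpha 0.05 (taken as two-sided), power 80%, correlation .015. Each pilot is taken as their own control, and 0.75 as the standardised paired difference.

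- Paired normal approximation: (1.96 + 0.8416)² / 0.75² = 13.95.
- Design effect for 18 pilots per airline and type: 1 + (18 − 1) × 0.015 = 1.255. The Protocol does not print this multiplier; it is inferred.
- 13.95 × 1.255 = 17.5, rounded up to 18.
- 18 × 2 = 36; 36 + 15 = 51; 51 × 4 = 204.

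All the stated figures reproduce. Without the .015 the number per type would be 14 (normal approximation) or 16 (paired t), so the adjustment adds pilots.

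**Do the routes overlap?** Example trips, assuming flights fill the hours from 0200 to 0559:

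| Trip | Route (i) | Route (ii) |
|---|---|---|
| 0500–1400, then 2130–0630 | yes | yes |
| 2200–0630, then a later 0500 start | yes | yes |
| 0030–0630 on two nights | yes | yes |
| 2200–0630 only | yes | no |
| 0500 start, then 1600–0100 | no | yes |

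The overlap is real but conditional: route (i) depends on flights, and duty start and end times alone do not settle it.

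**Power for one type inside one airline** (paired t, 0.75, no design effect), if 36 completers split unevenly:

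| Split | Pairs of the rarer type | Power |
|---|---|---|
| 18:18 | 18 | 85% |
| 22:14 | 14 | 74% |
| 25:11 | 11 | 61% |
| 30:6 | 6 | 32% |

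The stated 80% includes the design effect and these figures do not. On the plan's own basis, 18 pairs give 81%.

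**Power for what the Protocol sets out to test** (paired t, airline as a fixed effect):

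- All disrupted trips: 36 × 4 = 144 pairs, 144 − 4 = 140 degrees of freedom. Power exceeds 99.9% at 0.75. It also does so at 0.75/√2 = 0.53, which applies if 0.75 is scaled by the SD of a single measurement and the two trips are uncorrelated. With 80% power, 144 pairs detect about 0.24.
- One type pooled over airlines, 25:11 everywhere: 11 × 4 = 44 pairs, power over 99%.
- One type pooled over airlines, 30:6 everywhere: 6 × 4 = 24 pairs, 20 degrees of freedom, power about 94%.

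**How likely is a shortfall?** The documents give no type mix, so it has to be assumed. If all 51 recruits complete (an upper bound), the binomial chance of at least 18 of each type is:

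| Assumed mix | One airline | All four |
|---|---|---|
| 50:50 | 98% | 91% |
| 60:40 | 80% | 40% |
| 70:30 | 25% | 0.4% |

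**The case for a change.** The strongest case for a change is that eligibility definitions and recruitment targets belong in a protocol. The text itself names two conditions and sizes each at 18, and a missing type cannot be recovered after recruitment closes. The reserve of 15 is meant for attrition, so it cannot also be relied on to balance the types; at a 70:30 mix it would usually fail to. Reading the entry criterion as exactly one of the two routes does not help, because no trip meeting both is excluded.

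The facts in that argument stand, but the consequence is narrow. Requiring 18 per condition per airline is already a target; what is unwritten is how it is tracked. A coordinator confirms each pilot's eligibility before consent (sections 8.4 and 18), so a count by type needs no new procedure. Where a dual-route trip is counted is an analysis rule that commonly sits in an analysis plan, which is not shown here. The section 5 wording describes a theme from preliminary focus groups, not a study condition, so it does not conflict with route (ii).

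The obvious stricter remedies have costs of their own. Dropping the .015 removes the basis for 18. Letting dual-route trips count for neither type, while requiring 18 pairs of each and adding no pilots, can be unattainable: if a third of trips met both routes (an assumed share), 51 × (2/3) / 2 = 17 pilots per type would remain even with no attrition.

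**Conclusion.** The observation is accurate, but it calls for no change. The overlap, the missing counting rule and the absence of a quota are all there in the text. They are not a contradiction, because overlapping routes into one class of disrupted trips conflict with nothing in the stated aim or hypothesis. That comparison keeps over 99% power at 144 pairs, and a single type pooled over airlines keeps about 94% even at 30:6 in every airline.

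The stated 80% could be missed only for one type within one airline. The Protocol does not list that test as an objective, and the size of any shortfall depends on a type mix the documents do not give. The pooled estimate will reflect the mix of trips flown, which is acceptable for an observational study of normal scheduled operations that sets no comparison between airlines. Analysts would record the type of each trip, assign dual-route trips by one rule fixed before the results are seen, and report the mix.

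This rests on a two-sided paired analysis, 36 completers per airline, and 0.75 as the standardised paired difference; the full comparison holds at 0.53 as well. If the sponsor did intend confirmatory results by type within each airline, the shortfall would matter, but nothing in the Protocol says so.

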This category also includes the fourth most common theme, *Number of flights*. This theme refers to the number of flights within a duty period. While long-haul operations typically only involve one flight within a duty period, short-haul operations typically include two or more flights within a duty period. Most responses within this theme (41%) indicated that duty periods with more than four flights were considered fatiguing. However, approximately one-third (36%) of the codes in this theme indicated a preference for duty periods with two or fewer flights in order to avoid fatigue, with a quarter (23%) suggesting that any duty with more than one flight is automatically fatiguing due to the nature of the operations.

Rest opportunity. This category includes themes related to rest opportunities independent from the timing of those opportunities (see **Circadian disruption** for *Rest timing*) including *Rest Duration (Layover)* and *Rest quality*. *Rest quality* covered codes related to hotel sleep environment (e.g., noise, temperature). *Rest duration (layover)* was the second most common theme and refers to insufficient rest opportunity between duties. This theme was made up of codes including: SHORT REST (42%), and PERSONAL TIME (30%). SHORT REST referred to comments indicating that the FAR 117 minimum rest requirement of 10 hours is too short for sufficient sleep opportunity. PERSONAL TIME includes comments regarding the need for time to eat, exercise, wind down, and prepare for the next duty within the allocated rest period. In a short rest period, often there is not enough time for all these factors, leading to skipping important daily needs and/or reducing the amount of time available for sleep.

Schedule changes. This category emerged from the theme, *Unpredictability*, which covered codes such as SCHEDULE CHANGES (43%), PLANNED VS OPS (29%, planned schedules being different to operational reality), and EXTENSIONS and DIVERSIONS (28%). Schedule changes affected fatigue by extending flight or duty time, adding workload, and/or changing the timing of duty and rest opportunities.

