8.1 Protocol Overview

Scientific Merit. Please see attached ARC476 for scientific review and approval.

Specific Aims. The goal of this study is to provide insight into the influence of trips including circadian disruption on pilot cognitive performance, fatigue, sleepiness, sleep, and workload during short-haul operations across multiple airlines.

Hypotheses.

We aim to study pilots completing trips that include circadian disruption compared to trips that do not include circadian disruption.

- We hypothesize that cognitive performance, fatigue, sleepiness, and sleep outcomes will be worse during circadian disrupted trips compared to trips that do not involve circadian disruption.

Primary Outcome Measures.

Objective cognitive performance will be measured by the **psychomotor vigilance task (PVT)**, a simple reaction time task with outcome measures including mean reaction time, response speed (1/reaction time) and number of lapses (reaction time >500 ms). PVT performance will be measured at, or near, the timing of top of descent (TOD) during each flight.

Statistical Analyses.

The following factors will be also considered for inclusion in the analysis:

- **Schedule features:** flight duration, duty duration, duty start and finish times
- **Individual factors:** age, experience, chronotype (as measured by the morningness-eveningness questionnaire), sleep need
- **Sleep:** sleep duration, sleep loss, sleep start and finish times (all measured by the actiwatch)
- **Fatigue/alertness:** pre- and post-sleep and on-duty fatigue and alertness ratings (as measured by subjective scales)
- **Workload:** hassle factors encountered during flights and NASA TLX

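### The rule for a trip without circadian disruption (criterion b) tests only when duties begin or end, so a trip with an overnight duty that spans the whole window can satisfy both b and criterion a(i)

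*Protocol*

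**What the plan says.** Section 11 (Inclusion/Exclusion Criteria) requires each pilot to supply two kinds of trip.

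- **Criterion a, trip with circadian disruption.** It is "A trip containing one of the following types of WOCL infringement", and two types follow. Type (i), overnight FDPs, is "An FDP in which the pilot is operating one or more flights through the WOCL (0200-0559h"), taken relative to "home-base time or clock time". Nothing is said about when the FDP starts or ends. Type (ii), circadian switching, pairs an FDP that starts in 0000-0659h with one that ends in 0000-0659h, in either order, within a trip.
- **Criterion b, trip without circadian disruption.** The sentence under that heading is: "This trip must not contain any duties that are scheduled to begin or end between 0000h and 0659h relative to home-base time". It does not mention flights, and it uses home-base time only.

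Table 2 in Section 9 is to be "repeated for one circadian-disruption trip and one trip without circadian disruption". The hypothesis in Section 8.1 is that outcomes "will be worse during circadian disrupted trips compared to trips that do not involve circadian disruption".

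**The concern.** Criterion a(i) looks at what is flown, and criterion b looks only at the two ends of a duty. A duty that starts before the barred window and finishes after it has neither end inside it, yet it may hold exactly the flight that a(i) describes. The same trip could then be placed on either side of the comparison.

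That comparison is the primary aim (Section 5, last paragraph of the focus-group part) and the only hypothesis, and each pilot provides both trip types. Section 5 states that performance is worst in 0200-0559h. A control trip with a flight through those hours therefore carries the exposure that the study sets out to measure. The sample-size paragraph allots 18 of the 36 pilots per airline to night flying. For those pilots, such a control trip would put the same kind of exposure on both sides of the pair.

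**Working it through.** There is no figure in the plan to reproduce. The check compares the two rules in home-base time.

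**1. Shortest FDP that escapes b.** To pass b, an FDP that overlaps the WOCL must begin no later than 2359h and end no earlier than 0700h. From 2359h to 0700h is 7 h 01 min, or 421 min. Every such FDP contains all of 0200-0559h, so it can hold a flight through the WOCL. An overnight FDP of 7 h or less cannot escape.

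**2. Number of escaping start times.** Count minutes from midnight, with start s and length L. Passing b needs s ≤ -1 and s + L ≥ 420. That gives L - 420 start minutes for L above 420:

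| FDP length | Escaping start minutes |
|---|---|
| 7 h (420) | 0 |
| 8 h (480) | 60 |
| 10 h (600) | 180 |
| 12 h (720) | 300 |

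These counts show that the overlap is not empty and grows with FDP length. They treat all start minutes alike and say nothing about how often airlines schedule such duties.

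**3. One-flight FDPs.** Short-haul flights are "defined as flights under 6 hours duration", so at most 359 min. The non-flight duty needed to escape is at least 421 minus the flight time:

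- 359 min flight: 421 - 359 = 62 min
- 300 min flight: 421 - 300 = 121 min
- 240 min flight: 421 - 240 = 181 min

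Suppose 60 min from report to departure and 15 min from arrival to release (my assumption; the protocol gives neither). The flight must then last at least 421 - 75 = 346 min, so only 346 to 359 min qualifies, a 14-minute band.

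**4. A two-flight FDP on the same assumption.** Take 60 min report, a 2 h flight, a 1 h sit, a 5 h flight and 15 min release: 60 + 120 + 60 + 300 + 15 = 555 min, or 9 h 15 min. Starting at 2150h, the flights run 2250-0050h and 0150-0650h and the FDP ends at 0705h. The second flight covers all of 0200-0559h, so a(i) is met. The FDP begins before 0000h and ends after 0659h, so b is met too.

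**5. Criterion a(ii).** Either order of circadian switching includes an FDP that starts in 0000-0659h home-base time. Criterion b bars that on scheduled times, so b already excludes every a(ii) trip. The gap concerns a(i) alone.

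**6. Time basis.** Criterion a(i) accepts home-base or clock time; b accepts only the former. Section 5 itself notes shifts of up to three hours between time zones. Read clock time as local time. A duty of an Eastern-based pilot that starts at 0400h Pacific starts at 0700h home-base time, so its start passes b. A departure at 0500h Pacific then lies inside the clock-time WOCL. Whether that meets a(i) depends on whether *through* means all or any part of the window, which the protocol does not say.

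**7. Direction of the effect.** If a share p of control trips carries a fraction f of the true effect, the expected contrast is multiplied by (1 - p × f). That is toward zero if an effect exists. The document gives neither p nor f.

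**The case against.** The strongest reply is that exclusivity is already intended. Criterion b is headed as a trip without circadian disruption, criterion a defines circadian disruption, the two are joined as separate requirements, and Table 2 asks for one of each. A coordinator who confirms eligibility could reject an overnight trip on the heading alone. That stands as evidence of intent: the protocol does not direct anyone to enrol exposed controls, and a reader should not infer that it does. But the sentence under the heading is the only operative test, it has to be applied across four airlines, and read literally it admits these trips.

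A second reply is that the case must be rare. This is probably right, since short overnight duties are caught and a one-flight duty escapes only with much non-flight time or a flight close to 6 h. It limits the weight of the point but does not remove it.

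A third is that flight and duty information is recorded, so mislabelled trips can be found later, perhaps under an analysis plan that is not shown. They can be found, but an eligibility definition belongs to the protocol, and a later check needs a consistent definition to check against.

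A reader might also infer that long overnight duties are common because "short-haul operations typically include two or more flights within a duty period". That statement concerns the number of flights, not FDP length, and it is not about overnight duties.

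**Conclusion.** The point holds as a flaw in a stated rule. Criterion b is not the complement of a(i), and a trip with an FDP of at least 7 h 01 min that begins by 2359h, ends at 0700h or later and contains a flight through the WOCL satisfies both. Criterion b does exclude all a(ii) trips. The consequence is conditional: if such trips served as controls and the hypothesised effect exists, the primary contrast would be biased toward zero.

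No size can be put on that bias. A reader might take the start-minute counts as a share of contaminated control trips, or use them to shrink the planned effect size of 0.75 or to claim a loss of power. The document supports none of these, because it gives no schedule frequencies. The judgement that the frequency is low rests on the restriction to FDPs longer than 7 h. The worked two-flight duty rests on assumed report, sit and release times.

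**What to change.** Reconcile the two criteria in Section 11:

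- Add to b that the trip must also contain no FDP meeting a(i). Criterion a(ii) need not be added, because b already rules it out.
- State whether a flight *through* the WOCL must cover the whole window or any part of it.
- Use one stated time basis for both criteria. Otherwise, bringing a(i) into b also brings in its alternative of clock time.
- Before analysis, check each trip's label against the recorded flight and duty times.

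The cost is a short amendment and a check on data that Section 9 already collects. A few candidate control trips become ineligible, and possibly more if clock time or partial overlap is adopted. A relabelled control trip may leave a pilot without a pair: Section 8.5 allows more than two trips per pilot, but the schedule in Section 9 plans only two.
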